## **Retinal Examination**

Retinal examinations conducted by an ophthalmologist or optometrist will be performed during Screening and 6 and 12 months after treatment.

## **Electrocardiogram**

A 12-lead ECG will be obtained during Screening, and on Study Days 1, 8, and 15, and at early termination. At Screening, if a 12-lead ECG was done as part of the subject's previous routine care before signing the informed consent document and completed within 28 days before the administration of IP it does not need to be repeated. The subject should be relaxed and must be in a supine position at least 5 minutes before recording an ECG. The ECG readings are to be done in triplicate. The ECG will be reviewed by the Investigator (paper or electronic tracing) and will be available for comparison with subsequent ECGs by the Investigator. The following will be recorded on the electronic case report form (eCRF):

- PR Interval (msec)
- QRS Interval (msec)
- QT Interval (msec)
- QTcB (Bazett's formula) and/or QTcF (Fredericia's formula) Interval (msec)
- Heart Rate (BPM)
- RR Interval (msec)

Any ECG finding that is judged by the Investigator as a clinically significant change (worsening) compared to a baseline value will be considered an AE recorded and monitored.

## **Diagnostic Imaging**

An MRI scan of the chest, abdomen and pelvis will be performed at baseline, and 12 and 24 months post dose. If a specific contraindication exists for an MRI, then a CT scan may be performed instead. The same method of assessment and the same technique used at baseline should be used during follow-up evaluations.

---

\* A female of childbearing potential is a sexually mature female who 1) has not undergone a hysterectomy (the surgical removal of the uterus) or bilateral oophorectomy (the surgical removal of both ovaries) or 2) has not been postmenopausal for at least 24 consecutive months (ie, has had menses at any time during the preceding 24 consecutive months).

## Clinical Laboratory Tests

Samples for serum chemistry, hematology, urinalysis, troponin I, hemoglobin A1c, urinary cotinine, lipid and fatty acid analysis, coagulation, CECs, exploratory biomarker samples, and immunological/inflammation assessments will be taken at the times indicated on the Time and Events Schedule (Table 2) and will be evaluated by a central laboratory. Refer to the Laboratory Manual for detailed information on the collection, storage, and shipment of blood and urine samples.

### Serum Chemistry

Serum chemistry will be assessed at all visits and will include the following:

- Calcium
- Chloride
- Potassium
- Sodium
- Phosphorus
- Uric acid
- Alanine Aminotransferase (ALT; SGPT)
- Aspartate Aminotransferase (AST; SGOT)
- Creatinine
- Blood Urea Nitrogen (BUN)
- Total Bilirubin
- Indirect Bilirubin
- Direct Bilirubin
- Glucose
- Bicarbonate or Carbon Dioxide
- Lactic Dehydrogenase (LDH)
- Alkaline Phosphatase (ALK)
- Total Protein
- Albumin

### Hematology

Hematology tests will be performed at all visits and will include the following:

- Hemoglobin
- Red Blood Cell (RBC) Count
- Absolute Neutrophil Count (ANC)
- Hematocrit
- Platelet Count
- White Blood Cell (WBC) Count and Differential Count

### Urinalysis

Urinalysis will be performed at all visits and will include the following:

- Protein
- Ketones
- pH
- Microscopic (if gross findings are positive, then a microscopic examination, including WBCs/high power field (HPF) and RBCs/HPF, will be performed).
- Leukocyte Esterase
- Glucose
- Blood (hemoglobin)
- Specific Gravity
- Bilirubin

### Lipid Profile

A lipid profile will be performed at Screening and Study Days 1, 8, 15, and 29 and will include the following:

- Total Cholesterol
- Low Density Lipoprotein (LDL)
- High Density Lipoprotein (HDL)
- Very Low Density Lipoprotein (VLDL)
- Triglycerides

### Fatty Acids

Fatty acids assessment will be assessed at Screening and Study Days 1, 8, 15, and 29 and will include the following:

- Alpha-linolenic Fatty Acid
- Arachidate Fatty Acid
- Oleic Fatty Acid
- Linoleic Fatty Acid
- Stearic Fatty Acid

### Immunological/Inflammation Assessments

Immunological/inflammation assessment will include the following testing:

- Anti-HLA antibodies: Screening, Study Days 1, 8, 15, 29, Month 3, and at early termination.
- C-reactive protein: Screening, Study Days 1, 8, 15, and 29, and at Months 3 and 6.
- Quantitative assessment of serum immunoglobulins (IgA, IgM, and IgG): Screening, Study Days 1, 8, 15, 29, Month 3, and at early termination.

- VEGF: Screening, Study Days 1, 8, 15, and 29, Months 3 and 6, and at early termination.
- Cytokines IL-1 $\beta$ , TNF- $\alpha$ , IL-6, IL-8, IL-10, and TGF- $\beta$ : Screening, Study Days 1, 8, 15, and 29, Months 3 and 6, and at early termination.

### **Troponin I**

Troponin I will be measured during Screening, Study Days 1 and 8 prior to treatment, and 15.

### **Hemoglobin A1c**

Hemoglobin A1c will be measured during Screening, Study Day 1 and Months 3, 6, 9, 12, and 24.

### **Urinary Cotinine**

Urine samples will be collected and sent to the central laboratory to measure cotinine levels during Screening, on Study Days 1, 8 prior to treatment, 15, and Month 3.

### **Coagulation Tests**

Coagulation tests including assessment of PT/PTT, TAT, D-dimers, fibrinogen, TF-PCA and platelets will be assessed at Screening, on Study Days 1 and 8 prior to dosing with IP, approximately 2 hours post dose on Study 1 and 8 and also on Study Days 15 and 29.

### **Tryptase and Histamine**

Tryptase and histamine levels will be assessed on the day of treatment prior to dosing with IP and approximately 2 hours postdose on Study Days 1 and 8.

### **Circulating Endothelial Cells**

Circulating endothelial cells (CECs) will be measured at Screening, on Study Days 1 and 8 prior to dosing with IP, approximately 2 hours post dose on Study 1 and 8 and also on Study Days 15 and 29.

## **7. STUDY POPULATION**

### **7.1. Number of Subjects and Sites**

Up to 24 subjects will be enrolled at approximately 14 study centers in the US.

### **7.2. Inclusion Criteria**

Subjects must satisfy the following criteria to be enrolled in the study:

1. Males and females, 18 to 80 years of age at the time of signing the informed consent document.
2. Understand and voluntarily sign an informed consent document prior to any study related assessments/procedures are conducted.
3. Able to adhere to the study visit schedule and other protocol requirements.
4. Diabetes mellitus type 1 or 2.
5. Ischemic or neuro-ischemic diabetic foot ulcer with severity of Grade 1 (full thickness only) or Grade 2 on the Wagner Grading Scale ([Appendix A](#)) of greater than one month duration which has not adequately responded to conventional ulcer therapy.
6. Peripheral arterial disease with ankle-brachial index  $> 0.5$  and  $\leq 0.9$  or toe-brachial index  $> 0.35$  and  $\leq 0.7$ .
7. No planned revascularization or amputation over the next 3 months after Screening visit, in the opinion of the Investigator.
8. Screening should not begin until at least 14 days after a failed reperfusion intervention and at least 30 days after a successful mechanical intervention but longer wait times may be employed at the discretion of the investigator.
9. Subject can have stable angina, (Canadian Cardiovascular Society (CCS) Class I-II angina ([Appendix H](#))).
10. Subjects should be receiving appropriate medical therapy for hypertension and diabetes.
11. A female of childbearing potential must have a negative serum pregnancy test at Screening and a negative urine pregnancy test prior to treatment with study therapy. In addition, sexually active FCBP must agree to use 2 of the following adequate forms of contraception methods simultaneously such as: oral, injectable, or implantable hormonal contraception; tubal ligation; IUD; barrier contraceptive with spermicide or vasectomized partner for the duration of the study and the follow-up period.
12. Males (including those who have had a vasectomy) must agree to use barrier contraception (latex condoms) when engaging in reproductive sexual activity with FCBP for the duration of the study and the follow-up period.

### **7.3. Exclusion Criteria**

The presence of any of the following will exclude a subject from enrollment:

1. Any significant medical condition, laboratory abnormality, or psychiatric illness that would prevent the subject from participating in the study.
2. Any condition including the presence of laboratory abnormalities, which places the subject at unacceptable risk if he or she were to participate in the study.
3. Any condition that confounds the ability to interpret data from the study.
4. Subjects whom, in the judgment of the Investigator, are at elevated risk for the development of a malignancy. This judgment may be based on family history, history of industrial exposures, smoking history or other cancer risk factors.
5. Known to be positive for human immunodeficiency virus.
6. Pregnant or lactating females.
7. Subjects with a body mass index  $> 40$  at Screening.
8. AST or ALT  $> 2.5 \times$  the upper limit of normal (ULN) at Screening.
9. Estimated Glomerular Filtration Rate (eGFR)  $< 45 \text{ mL/min/1.73 m}^2$  at Screening calculated using the Modification of Diet in Renal Disease Study equation ([Levey, 2006](#)) or history of eGFR decline  $> 15 \text{ mL/min/1.73 m}^2$  in the past year.
10. Alkaline phosphatase  $> 2.5 \times$  the ULN at Screening.
11. Bilirubin level  $> 2 \text{ mg/dL}$  (unless subject has known Gilbert's disease) at Screening.
12. Untreated chronic infection or treatment of any infection with systemic antibiotics, including the ulcer site, within 4 weeks prior to dosing with IP.
13. Known osteomyelitis.
14. Ulcer that has decreased or increased in size by  $\geq 50\%$  during the screening period.
15. Uncontrolled hypertension (defined as diastolic blood pressure  $> 100 \text{ mmHg}$  or systolic blood pressure  $> 180 \text{ mmHg}$  during Screening at 2 independent measurements taken while subject is sitting and resting for at least 5 minutes).
16. Poorly controlled diabetes mellitus (hemoglobin A1c  $> 10\%$ ).
17. Untreated proliferative retinopathy.
18. History of malignant ventricular arrhythmia, CCS Class III-IV angina pectoris, myocardial infarction/PCI (percutaneous coronary intervention)/CABG (coronary artery bypass graft) in the preceding 6 months, pending coronary revascularization in the following 3 months, transient ischemic attack/cerebrovascular accident in the preceding 6 months, and/or New York Heart Association [NYHA] Stage III or IV congestive heart failure ([Appendix C](#)).
19. Abnormal ECG: new right bundle branch block (BBB)  $\geq 120 \text{ msec}$  in the preceding 3 months.
20. Uncontrolled hypercoagulation.
21. Life expectancy less than 2 years due to concomitant illnesses.
22. In the opinion of the Investigator, the subject is unsuitable for cellular therapy.

[figure not shown]
23. History of malignancy within 5 years except basal cell or squamous cell carcinoma of the skin or remote history of cancer now considered cured or positive Pap smear with subsequent negative follow-up.
24. History of hypersensitivity to any of the components of the product formulation (including bovine or porcine products, dextran 40, and dimethyl sulfoxide [DMSO]).
25. Disorders or allergies precluding the use of radiographic contrast or renal insufficiency severe enough to contraindicate the use of radiographic contrast.
26. Subject has received an investigational agent—an agent or device not approved by the US Food and Drug Administration (FDA) for marketed use in any indication— within 90 days (or 5 half-lives, whichever is longer) prior to treatment with study therapy or planned participation in another therapeutic study prior to the completion of this study.
27. Subject has received previous gene or cell therapy.

## 8. DESCRIPTION OF STUDY TREATMENTS

### 8.1. Description of Investigational Product

PDA-002 is a novel product being developed specifically for local injectable delivery applications of PDA-001 cells. PDA-001 is Celgene Cellular Therapeutics' (CCT) original product and has been used in clinical studies for Crohn's disease, sarcoidosis, multiple sclerosis, rheumatoid arthritis, and stroke indications that require systemic administration. PDA-001 and PDA-002 have the same drug substance process (production of cells), but different drug product process (formulation and cryopreservation) and properties.

[figure not shown]
PDA-002 is characterized as a cellular angiogenic and immune modulating agent with therapeutic potential. The product contains a mesenchymal-like cell population derived from normal, full-term human placental tissue. The cells are culture-expanded in vitro as a plastic-adherent, undifferentiated, cell population that expresses the nominal phenotype CD34-, CD10+, CD105+, and CD200+. The cells constitutively express moderate levels of HLA Class I and undetectable levels of HLA Class II.

### 8.2. Treatment Administration and Schedule

PDA-002 will be provided in 5-mL units at a concentration of 20 million cells/mL and will be diluted with normal saline to achieve the desired concentration based on dose level. Product thawing, dilution, and infusion will be performed according to sponsor provided instructions.

Investigational product will be administered on Study Days 1 and 8. No more than 1 subject may begin treatment in any 48-hour period. 

Subjects will receive IP administered as fifteen 0.33 mL injections (approximately 5 mL total) in the treatment leg. The target region is suggested to be below the knee and above the ankle. Injections are suggested to be at least 1 cm apart horizontally and laterally and at a depth of approximately 1 to 4 cm. It is suggested that they be administered in a pattern of 3 x 5 injections around the leg and injections should not be near a blood vessel.

PDA-002 is not intended for IV administration. When the injection is given, the syringe should be aspirated to avoid inadvertent venous administration. If any blood is aspirated into the

[figure not shown]

syringe, the needle is to be pulled out a little, and the syringe reaspirated. If no blood is seen, the IP may be injected.

Vital signs (including heart rate, respiration, blood pressure, body temperature, and pulse oximetry) will be monitored prior to starting the injections and every 15 minutes for a minimum of 2 hours after completion of the injections. Blood samples for tryptase and histamine, coagulation assessments, CECs, and exploratory biomarkers will be collected approximately 2 hours after the injections have been completed.

Physician support must be available onsite. The investigational centers must also offer appropriate supplemental services that support clinical care to ensure that the protocol specified monitoring will be followed.

**Administration Instructions.** Under aseptic conditions, PDA-002 will be injected IM, below the knee, at 15 sites on the affected limb on Study Days 1 and 8. The injection volume will be 0.33 mL. A 1.0 mL syringe with a 22-gauge 1.5-inch long needle will be used to inject the IP.

**Please refer to the Study Manual for more detailed instructions and a recommended injection grid.**

**Note:** For this study, all  $\geq$  Grade 3 allergic reactions associated with the use of IP must be reported to CCT as an SAE within 24 hours of the Investigator's knowledge of the event.

#### **8.2.1. Discontinuation**

The following events are considered sufficient reasons for discontinuing a subject from further treatment with the IP and/or from the study:

- Adverse event(s)
- Withdrawal of consent
- Death
- Lost to follow-up
- Protocol violation
- Inclusion/exclusion criteria not met

The reason for discontinuation should be recorded in the eCRF and in the source documents.

[figure not shown]
Patients who discontinue will have laboratory assessments performed as specified in the Early Termination Column in the Table of Events ([Table 2](#)) using the Unscheduled Visit Kit in addition to an ECG. Those who discontinue prior to Visit 7 will also have Exploratory Biomarker Sample Collection.

### 8.3. Method of Treatment Assignment

Eligible subjects will be assigned to a cohort based on the order in which they enter the study according to the dose escalation scheme (Section 4.1).

[figure not shown]
The pharmacist/designee at the study site will prepare the appropriate IP and deliver it to the personnel performing the injections. **Pharmacists should consult the pharmacy manual for detailed instructions on the preparation and handling of PDA-002 for this study**

### 8.4. Packaging and Labeling

[figure not shown]
The syringe rack label, affixed subsequently to thawing/dilution and prior to administration, will provide expiry, volume, and handling instructions.

### 8.5. Investigational Product Accountability and Disposal

PDA-002 is regulated by the United States FDA as a human cellular product. The FDA (21 Code of Federal Regulations [CFR] 1271.290) requires that a record-keeping system be used to track human cellular and tissue-based products from the donor to the consignee and vice versa, or any other final disposition (for example, shipment was lost or the integrity of the unit was compromised.) In accordance with this regulation, CCT has established a tracking system for PDA-002.

For each unit of PDA-002 that is administered, it is important to maintain records sufficient to permit prompt identification of the recipient. At no time will the identification of the donor be known by the subjects in the clinical study.

Celgene will instruct the Investigator on the return, disposal and/or destruction of investigational product and/or medical device materials if applicable.

#### **8.6. Investigational Product Compliance**

Accurate recording of all IP administration (including dispensing and dosing) will be made in the appropriate section of the subject's eCRF and source documents.

The Investigator(s) or designee(s) is responsible for accounting for all IP that is issued to the investigative site during the course of the study.

## **9. CONCOMITANT MEDICATIONS AND PROCEDURES**

All medications (prescription and non-prescription), treatments and therapies taken from 30 days prior to Visit 1 (the Screening/Baseline Visit) until Month 24 must be recorded on the appropriate page of the eCRF.

### **9.1. Permitted Concomitant Medications and Procedures**

All subjects are to receive standard medical care for the treatment of chronic DFU and its complications unless contraindicated. An effort should be made to maintain the patient's standard medical care for at least the first 12 Weeks following the initiation of dosing unless changes are necessary to ensure the best care for the patient.

### **9.2. Prohibited Concomitant Medications and Procedures**

There are no prohibited concomitant medications in this study except for investigational agents.

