### 11.2.3. Causality

The Investigator must determine the relationship between the administration of IP and the occurrence of an AE/SAE as Not Suspected or Suspected as defined below:

Not Suspected: The temporal relationship of the adverse event to IP administration makes **a causal relationship unlikely or remote**, or other medications, therapeutic interventions, or underlying conditions provide a sufficient explanation for the observed event.

Suspected: The temporal relationship of the adverse event to IP administration makes **a causal relationship possible**, and other medications, therapeutic interventions, or underlying conditions do not provide a sufficient explanation for the observed event.

If an event is assessed as suspected of being related to a comparator, ancillary or additional IP that has not been manufactured or provided by Celgene, please provide the name of the manufacturer when reporting the event.

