10.3.3. Secondary Endpoint 3 – Time to Major Amputation

Descriptive statistics for time to major amputation (above the ankle) of treated leg, time to doubling of index ulcer total surface area from baseline in treated leg, de novo gangrene in treated leg, time to reopening of closed ulcer, time to index ulcer total surface area reduction from baseline by 50%, and time to ulcer healing will be presented by cohort.

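### An approved cell or gene product may be used during follow-up, and the SAP neither separates results after such use nor reliably lists it

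*Protocol*

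**What the plan says.** **At entry.** Protocol Section 7.3, exclusion 27, rules out a candidate if "Subject has received previous gene or cell therapy". Exclusion 26 deals with investigational agents and defines one as "an agent or device not approved by the US Food and Drug Administration (FDA) for marketed use in any indication".

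**On study.** Section 9.2 states: "There are no prohibited concomitant medications in this study except for investigational agents". Its heading mentions procedures, but the text restricts none. Section 9.1 adds a softer request: "An effort should be made to maintain the patient's standard medical care for at least the first 12 Weeks following the initiation of dosing", with an exception where the patient's best care needs a change. Under Section 9, therapies taken from 30 days before Visit 1 "until Month 24 must be recorded on the appropriate page of the eCRF".

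**In the SAP.** Ulcer number and index-ulcer size (10.3.2) and Wagner grade (10.3.4) are summarised by cohort at each visit to Month 24. Section 10.3.3 gives descriptive statistics for the time-to-event outcomes, including 50% reduction, and "time to ulcer healing will be presented by cohort". Section 11.3 summarises change from baseline in laboratory parameters, anti-HLA antibodies among them, by cohort and visit. Section 8.4.2 counts a medication as concomitant only if it began no later than treatment discontinuation. The last planned dose is on Day 8.

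**The concern.** Subjects enter with no history of gene or cell therapy, but nothing in the protocol keeps that true afterwards for approved products. They are enrolled because the ulcer has not responded adequately to conventional therapy, so a later change of ulcer treatment is foreseeable over 24 months.

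There is no control arm and cohorts hold 3 to 6 subjects. If an ulcer closes after another cell product, the subject appears as healed in a PDA-002 dose cohort with nothing to mark the difference. A new anti-HLA antibody after such a product would likewise appear as a change from baseline under PDA-002. The exposure should be in the eCRF, but no visible SAP rule uses that record, and the one table meant to show other medications can leave out a product started after Day 8. At stake is how the small-cohort efficacy and immunology summaries are read.

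**Working it through.** **Step 1: what is open on study.** Exclusion 27 is a condition on history at enrolment. Section 9.2 bans investigational agents only. Under exclusion 26, a product approved in any indication is not investigational, even if it is used for another purpose. Section 9.1 asks for an effort over 12 weeks and has an exception. Together these leave an approved cell or gene product permitted after dosing, with a soft discouragement for the first 12 weeks and none from then to Month 24.

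**Step 2: what the SAP does with it.**
- The Efficacy Evaluable population (SAP 5.2.1) depends on receiving IP and having a baseline and a post-baseline assessment, not on other therapy.
- SAP 10.3.2 to 10.3.4 and 11.3 contain no censoring, exclusion, flag or sensitivity analysis for another cell or gene product.
- SAP 8.4.2 closes at treatment discontinuation, while protocol Section 9 records to Month 24. A product started after Day 8 can be in the database and absent from the table.
- SAP Section 14, on changes from the protocol's analyses, does not mention the matter.
- SAP 5.1 and 16.1 to 16.2 are partly redacted. Their headings concern reporting and date conventions.

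**Step 3: the plan's own figure.** 4 cohorts × 6 subjects = 24, which matches the stated maximum. There is no power calculation to reproduce.

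**Step 4: weight of one subject.** One healer changes the proportion healed by 1/n:
- n = 3: 1/3 = 33.3 points
- n = 6: 1/6 = 16.7 points
- n = 24: 1/24 = 4.2 points

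**Step 5: chance that at least one subject is exposed.** The documents give no usage rate, so u is assumed. P = 1 − (1 − u)^n:

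| Assumed use u | n = 6 | n = 24 |
|---|---|---|
| 2% | 11% | 38% |
| 5% | 27% | 71% |
| 10% | 47% | 92% |
| 20% | 74% | 99.5% |

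**Step 6: chance of at least one healer after such a product in a cohort of 6.** With assumed use r and assumed healing h among users, P = 1 − (1 − r·h)^6:
- r = 2%, h = 30%: 1 − 0.994^6 = 3.5%, about 4%
- r = 10%, h = 30%: 1 − 0.97^6 = 16.7%
- r = 20%, h = 50%: 1 − 0.90^6 = 46.9%
- r = 30%, h = 50%: 1 − 0.85^6 = 62.3%

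These count everyone who heals after the product, including those who would have healed without it. They are therefore an upper limit on healing caused by the other product under each pair of assumptions.

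**Step 7: anti-HLA window.** Protocol Section 6.4.5 schedules "Anti-HLA antibodies: Screening, Study Days 1, 8, 15, 29, Month 3, and at early termination". Only exposure before the Month 3 or early-termination sample can affect these results. Section 9.1's 12-week request covers nearly all of that period. Ulcer outcomes are open to Month 24.

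**The case against.** **No contradiction.** A reader might infer that exclusion 27 and Section 9.2 contradict each other. They do not, strictly: one fixes history at entry and the other governs care on study, and the documents never say that the entry condition must persist. Open background care is part of the design. This stands. The point is a gap between two provisions and a missing analysis rule.

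**Section 9.1 already discourages changes.** This also stands for the first 12 weeks, and it weakens the anti-HLA part considerably. It is not a prohibition and leaves most of the 24 months untouched. The documents do not say that any marketed product induces anti-HLA antibodies, and they name no marketed cell product.

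**The DLT count.** A reader might infer that another product could remove events from the DLT count, because Section 11.2.3 classes an event as not suspected where "other medications, therapeutic interventions, or underlying conditions provide a sufficient explanation for the observed event". That is how causality assessment works for every concomitant treatment, and an internal DMC reviews all safety information. The documents show no specific effect on the DLT count or the MTD.

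**Growth-factor products.** Exclusion 27 names only gene and cell therapy. Growth factors are not barred at entry, so no mismatch exists for them.

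**Attribution is weak anyway.** Efficacy is descriptive, no formal comparison is planned, and protocol Section 4.2 accepts that numbers are too small to determine benefit unless responses are dramatic. With standard care and debridement, no healing can be credited to PDA-002 alone. That limits the severity. It does not justify leaving a known, recorded exposure invisible in cohorts of 3 to 6.

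**Stopping at first use can bias.** Subjects given another product are likely to be those whose ulcers are not closing. Dropping their later results could flatter the cohort. At an assumed 30% use, 0.30 × 6 = 1.8, so about 2 of 6 subjects would be cut short. This stands, and it rules out the truncated summary as the main one.

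**Conclusion.** The concern holds as a gap in design and analysis. An approved cell or gene product may be used during follow-up. The SAP does not separate ulcer or anti-HLA results after such use, and its concomitant-medication definition can keep a product started after Day 8 out of the table.

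One affected subject moves a cohort's healing rate by 17 points (n=6) or 33 points (n=3). That needs no assumption beyond cohort size. How often it would happen is unknown: about 4% to 62% for at least one healer after such a product in a cohort of 6, on assumed use of 2% to 30% and assumed healing of 30% to 50%. A reader might take the upper end as the chance of healing falsely credited to PDA-002. The documents do not support that, since the rates are assumed and some of those subjects would have healed anyway.

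The anti-HLA part is limited to exposure before Month 3 or early termination. The affected efficacy endpoints are secondary and descriptive, and no effect on the MTD is shown. The change is still worth making because it draws on information the protocol already requires to be recorded.

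**What to change.** - **Protocol 7.3 and 9.2:** the sponsor should reconcile the two sections and state whether the entry condition on gene and cell therapy is meant to continue on study. Which therapies to allow is the sponsor's decision.
- **SAP 8.4.2:** extend the concomitant-therapy summary to Month 24, in line with protocol Section 9, and flag other cell or gene products with their start dates.
- **SAP 10.3.2 to 10.3.4:** keep the summary regardless of such use as the main one. Add a supplementary summary of ulcer size, 50% reduction, healing and Wagner grade up to first use, with a note that stopping at first use may be informative.
- **SAP 11.3:** add an anti-HLA display that leaves out samples taken after such exposure.

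The cost is a wording reconciliation, a few SAP lines and a few extra tables. Therapies are already to be recorded to Month 24. The sponsor should check that the eCRF shows which leg was treated, because Section 9 does not say so.
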